
 
To investigate the effect of 60 mg three times daily doses of GSK2982772 on bone and synovial parameters as measured by MRI and DCE-MRI in subjects with moderate to severe Rheumatoid Arthritis.
 
	
 
Change from baseline in Magnetic Resonance Imaging (MRI) parameters in the most affected hand/wrist. MRI parameters may include assessment of bone erosions, synovitis, bone oedema and joint space narrowing as assessed in the OMERACT-RAMRIS (Outcome Measures in Rheumatology, Rheumatoid Arthritis Magnetic Resonance Image Scoring System) scoring system, the RAMRIQ (Rheumatoid arthritis MRI quantitative) scoring system, the modified CARLOS (Cartilage Loss Scoring System) and additional exploratory endpoints as data permit.
 
Change from baseline in synovial inflammation as measured by dynamic contrast enhanced (DCE)-MRI in the most affected hand/wrist: 
 
Exchange rate (<math>K^{trans}</math>)
 
Interstitial volume (<math>V_e</math>)
 
Plasma volume (<math>V_p</math>)
 
Initial rate of enhancement (IRE)
 
Maximal signal intensity enhancement (ME)
 
Joint volume
 
Enhancing volume
 
 
 

 
To investigate the effect of 60 mg three times daily doses of GSK2982772 on clinical disease activity in subjects with moderate to severe Rheumatoid Arthritis.
 
	
 
Change from baseline in Disease Activity Score (DAS) 28-CRP scores.
 
Proportion of subjects achieving categorical DAS28-CRP response (moderate/good EULAR response) at each assessment time points.
 
Proportion of subjects achieving categorical ACR20/50/70 response.
 

 
To investigate the effect of 60 mg three times daily dosing of GSK2982772 on methotrexate (MTX) concentrations.
 
	
 
Plasma concentrations of MTX pre-dose GSK2982772 on Days 1, 8, and 43 (Week 6).
 

Exploratory	

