	
 
• Exchange rate (<math>K^{trans}</math>)
 
• Interstitial volume (<math>V_e</math>)
 
• Plasma volume (<math>V_p</math>)
 
• Initial rate of enhancement (IRE)
 
• Maximal signal intensity enhancement (ME)
 
• Joint volume
 
• Enhancing volume
 

 
• To investigate the effect of 60 mg three times daily doses of GSK2982772 on clinical disease activity in subjects with moderate to severe Rheumatoid Arthritis.
 
	
 
• Change from baseline in Disease Activity Score (DAS) 28-CRP scores.
 
• Proportion of subjects achieving categorical DAS28-CRP response (moderate/good EULAR response) at each assessment time points.
 
• Proportion of subjects achieving categorical ACR20/50/70 response.
 

 
• To investigate the effect of 60 mg three times daily dosing of GSK2982772 on methotrexate (MTX) concentrations
 
	
 
• Plasma concentrations of MTX pre-dose GSK2982772 on Days 1, 8, and 43 (Week 6).
 

Exploratory	

 
• To investigate the effect of 60 mg three times daily doses of GSK2982772 on inflammatory biomarkers in synovial tissue in subjects with moderate to severe Rheumatoid Arthritis.
 
	
 
• Change from baseline in CD68+ macrophages, CD55+ fibroblast-like synoviocytes and a number of infiltrating CD3, CD22, CD138 inflammatory cells, and synovial inflammatory biomarkers including, but not limited to VEGF, IL-1<math>\beta</math>, IL-6, TNF<math>\alpha</math>, and MMP-1.
 

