Potential Risk of Clinical Significance	Summary of Data/Rationale for Risk	Mitigation Strategy
		
inclusion in the study.
 
Withdrawal Criteria:
 
 
If a female subject should become pregnant during the study, study medication should be discontinued. The subject will be followed to determine the outcome of the pregnancy. Any pregnancy complication or elective termination of a pregnancy will be reported as an AE or SAE.
 

Drug Interaction	
Non-clinical data:
 
In vitro studies with GSK2982772 assessing potential drug-drug interactions with Cytochrome P450 3A4 (CYP3A4) substrates, P-glycoprotein (Pgp) inhibitors and OAT3 substrates were completed. To date, formal drug interaction studies in humans have not been performed with GSK2982772.
 
There is a low risk that GSK2982772 could be a perpetrator of OAT3 substrates. MTX is an OAT3 substrate in which GSK2982772 could potentially impair the clearance of MTX.
 
There is a low risk that GSK2982772 could be an inducer of CYP3A4 and therefore may lower circulating levels of concomitant medications that are metabolised by CYP3A4 when co administered with GSK2982772.
 
GSK2982772 is a Pgp substrate and therefore co administration with concomitant medications that are Pgp inhibitors could increase circulating levels of GSK2982772. See Section 4.3.6 of the GSK2982772 IB [GlaxoSmithKline Document 2014N204126_02].
	
Subject Selections:
 
 
Subjects who are taking concomitant medications known to inhibit Pgp or are CYP3A4 narrow therapeutic index (NTI) substrates will be excluded from the study. See Section 6.11.2 for a comprehensive list of medications.
 
 
Subject Monitoring:
 
 
Subjects' concomitant medication usage will be reviewed prior to inclusion and monitored throughout the study.
 
Subjects should be monitored throughout the study for potential effects of interaction between GSK2982772 and other concomitant medications.
 
PK sample collection to evaluate the potential interaction of GSK2982772 and MTX will be performed throughout the study.
 
Subjects should be monitored for potential effects of interaction between GSK2982772 and MTX.
 
Clinical laboratory results (e.g., liver function tests) are routinely being monitored throughout the study.
 

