## **6.11. Concomitant Medications and Non-Drug Therapies**

### **6.11.1. Permitted Medications and Non-Drug Therapies**

Selected medications for the treatment of RA may be taken, with specific requirements listed in [Table 1](#), and as long as they are not prohibited (Section [6.11.2](#)). All concomitant medications taken during the study will be recorded in the source document and CRF. The minimum requirement is that drug name and dates of administration are recorded.

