**Table 1 Specific Requirements for Permitted Medications During the Study**

Drug	Requirement
Methotrexate	Stable dose regimen (up to 25 mg/week) for at least 12 weeks prior to screening and remain on this dose throughout the study (unless dose must be reduced because of a safety concern). MTX should ideally be taken on the same day of week and at approximately the same time of day throughout the study.
Sulfasalazine	Stable dose regimen for at least 12 weeks prior to screening and throughout the study.
Hydroxychloroquine or chloroquine	Stable dose for at least 12 weeks prior to screening and throughout the study.
Leflunomide	Stable dose for at least 12 weeks prior to screening and throughout the study.
Folate supplements (minimum of 5 mg/week)	If a subject is on folate supplements with MTX treatment, they must be on a stable dose regimen for at least 4 weeks prior to randomization and throughout the study.
Other oral anti-rheumatic therapies such as non-steroidal anti-inflammatory drugs (NSAIDs), oral glucocorticoids (e.g., prednisolone $\leq$ 10 mg /day. See Appendix 3 for equivalent doses).	Stable dose regimen for at least 4 weeks prior to screening and throughout the study (unless reduction required due to adverse effects). Omit dose on the morning prior to study visits until after joint assessments.

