11. Blood samples for inflammatory biomarkers, mRNA and target engagement. See laboratory manual for full details on sample collection, handling and shipment.
12. PK blood samples for GSK2982772 will be taken pre-dose on Days 8 and 43. Post-dose serial PK samples will be taken on Days 1, 8 and Day 43 at the following time points: 1, 2, 4, and 6 hours. A trough PK sample will be taken on Day 85 or at Early Withdrawal.
13. Only applicable if subjects are on MTX: PK blood samples for MTX will be taken pre-dose GSK2982772 on Day 1 (MTX alone), on Days 8 and 43 (MTX + GSK2982772). Subjects who are on MTX should ideally take their MTX dose on the same day of the week at approximately the same time of the day throughout the study. In addition, the Day 1, 8 and 43 visits should ideally be on the same day of the week.
14. A PGx blood sample is collected at the baseline visit, after the subject has been randomised and provided informed consent for genetic research. If the sample is not collected at the baseline visit, it can be collected at any time during the study after randomisation.
15. Synovial biopsies are optional.
16. Biopsy (if applicable) and MRI only are required at Early Withdrawal visit if subject withdraws after at least 14 days of treatment and prior to Day 43. If a subject withdraws between Days 43 and 57, an MRI is not required at the Early Withdrawal visit. If a subject withdraws on Day 57 or after, an MRI should be performed at the Early Withdrawal visit. A window allowance of  $\pm 3$  days of Early Withdrawal visit is allowed to perform the MRI.
17. Visit windows during the treatment period are relative to Day 1.
18. If a subject withdraws from the study, every effort will be made for the subject to complete an Early Withdrawal visit prior to the Follow Up visit.
19. Follow-up visit should be completed 28 days ( $\pm 3$  days) after the last dose of study medication.
20. MRI (and if applicable; a biopsy) may be performed during the screening window as an additional visit (if required) up to 7 days before Day 1 to allow sites flexibility in scheduling. The MRI must be completed prior to synovial biopsy (if performed on the same joint). The site should be reasonably confident that the subject has fully qualified for the study (e.g., screening clinical labs, vital signs, physical examination, etc.) before the MRI (and if applicable: a biopsy) is/are performed.

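### Methotrexate samples are timed to the GSK2982772 dose and not to the weekly methotrexate dose, so the protocol does not ensure that the methotrexate interaction objective can be answered

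*Protocol*

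**What the plan says.** The secondary objective is "To investigate the effect of 60 mg three times daily dosing of GSK2982772 on methotrexate (MTX) concentrations". Its only endpoint, in the synopsis and in Section 3, is "Plasma concentrations of MTX pre-dose GSK2982772 on Days 1, 8, and 43 (Week 6"), one sample per visit. Footnote 13 of the Time and Events Table repeats that anchor: "PK blood samples for MTX will be taken pre-dose GSK2982772 on Day 1 (MTX alone), on Days 8 and 43 (MTX + GSK2982772").

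Table 1 in Section 6.11.1 shows that MTX is weekly background treatment: "Stable dose regimen (up to 25 mg/week"). It adds "MTX should ideally be taken on the same day of week and at approximately the same time of day throughout the study". Footnote 13 makes a matching request about visits: "In addition, the Day 1, 8 and 43 visits should ideally be on the same day of the week". The Time and Events Table gives Days 8 and 43 a window of ±3 days.

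On records, Section 6.7 requires the date, time and weekly dose of MTX in the diary cards and the CRF, and Section 7.5.1 requires the actual date and time of each sample. Diary cards are first dispensed on Day 1.

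Section 4.6.1 gives the reason for the objective. GSK2982772 might impair MTX clearance, a risk rated low, and no formal human interaction study has been done. Among its monitoring measures is "PK sample collection to evaluate the potential interaction of GSK2982772 and MTX will be performed throughout the study".

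**The concern.** The concentration of a drug taken once a week depends chiefly on how long ago it was taken. The protocol fixes the sample relative to the other drug. It asks for a constant MTX weekday and a constant visit weekday, but it never relates the two.

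Two separate weaknesses follow. First, the length of the MTX-to-sample interval is open even under full compliance, so a subject's three samples may all come too late to show anything. Second, the interval is not firmly held constant, so the Day 1 reference and the on-treatment samples may differ for reasons unrelated to GSK2982772.

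At stake is whether the objective yields information. Values near zero at all visits could be read as absence of an interaction when they show nothing either way. A shifted interval could mimic or hide an effect in an individual subject.

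**Working it through.** The protocol gives no half-life, assay limit or sample size for this objective, so there is no figure to reproduce. The check takes the schedule from the protocol and adds two assumptions, shown as ranges.

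**Inputs from the protocol:** weekly MTX (168 h cycle); samples on Days 1, 8 and 43 before the morning GSK2982772 dose; ±3 days at Days 8 and 43; 16 active subjects in the TID cohort (Section 9.2.1).

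**Assumptions, not in the protocol:** MTX half-life 3 to 15 h; ratio of peak concentration to the lower limit of quantification (LLOQ) 100 to 1000; single-exponential decline.

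1. *Schedule.* 8 − 1 = 7 and 43 − 1 = 42 days, both multiples of 7. At the nominal days all three visits fall on one weekday, so a subject with a fixed MTX weekday and clock time has one constant interval. Its length can be anything from 0 to 168 h.

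2. *A compliant subject with late samples.* MTX is taken on the evening of the visit weekday, about 12 h after the morning sample. The preceding MTX dose is then 168 − 12 = 156 h before each sample, at all three visits.

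3. *Decay.* Fraction remaining = 0.5^(t / half-life). Change caused by a 24 h shift = 2^(24 / half-life).

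4. *Measurable part of the week.* Hours = log2(peak/LLOQ) × half-life, divided by 168.

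| Assumed half-life | Left at 24 h | Left at 96 h | Left at 156 h | 24 h shift | Share of week measurable (ratio 100 to 1000) |
|---|---|---|---|---|---|
| 3 h | 0.4% | about 2e-10 (fraction) | about 2e-16 (fraction) | 256-fold | 12% to 18% |
| 8 h | 12% | 0.02% | 0.0001% | 8-fold | 32% to 47% |
| 10 h | 19% | 0.13% | 0.002% | 5.3-fold | 40% to 59% |
| 15 h | 33% | 1.2% | 0.07% | 3.0-fold | 59% to 89% |

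For example, at 15 h: 156 / 15 = 10.4 half-lives, and 0.5^10.4 = 0.0007. At 3 h: 156 / 3 = 52 half-lives.

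5. *Number of informative subjects.* If the MTX weekday is unrelated to the visit weekday and all 16 active subjects take MTX, the expected number with measurable samples runs from 16 × 0.12 = 1.9 to 16 × 0.89 = 14.2. Inclusion criterion 7 also admits subjects on other non-biologic DMARDs, so the real number would be lower to the extent that subjects are not on MTX.

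**The case against.** The strongest reply is that the weekday requests do the essential work. If they are followed, each subject's interval is the same at all three visits, which is what a comparison with Day 1 needs. This stands. A reader might infer that the objective cannot be answered, or that any change from Day 1 mainly reflects time since MTX. The protocol supports neither: subjects who happen to take MTX shortly before their visits can give usable pairs, and changing intervals require a departure from the weekday requests.

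A second reply is that the times are known. A reader might take the general rule in Section 6.11.1, "The minimum requirement is that drug name and dates of administration are recorded", to mean that MTX clock times are not collected. Section 6.7 sets a stricter rule for MTX, and sample times are recorded too, so elapsed time can be recovered for selection or adjustment. This also stands, with two limits. A recorded time does not restore information to a sample taken too late. And the intake before the Day 1 sample precedes the first diary card; the CRF may capture it, but the protocol does not say so.

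Third, the randomised placebo group follows the same schedule, so random drift mostly adds noise and does not push the comparison one way. That is fair, although several-fold noise in a small group still costs a great deal.

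Fourth, a reader might think that the Section 4.6.1 monitoring rests on these samples alone. It does not: clinical monitoring for interaction effects and routine laboratory tests are listed as well.

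Fifth, the Study Reference Manual or laboratory manual might set MTX timing; neither is shown. However, Section 7 places assessment timing in Section 7.1, and Section 7.5.1 refers MTX sampling to the same table, citing the manual for collection, processing, storage and shipping.

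**Conclusion.** The point holds as a gap in design. The protocol does not ensure that the MTX objective can be answered, and it leaves the number of informative subjects to chance: roughly 2 to 14 of 16 on the assumptions above, if all take MTX.

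That 0 to 168 h is open under full compliance follows from the protocol alone. The sizes do not: they rest on the assumed half-life, and any statement that a sample is unmeasurable also needs an assay limit that the protocol does not give. The 256-fold figure is the extreme of the range; at a 15 h half-life the same 24 h shift is about 3-fold.

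This is one secondary objective in an unpowered study whose primary purpose is safety, so the consequence is limited. It is still worth correcting, because the remedy is cheap and sampling time is a matter of conduct that no later analysis can repair. How ratios are reported and how values below the assay limit are handled belong to the analysis plan and are not criticised here.

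**What to change.** In footnote 13 and Section 7.5.1, for subjects on MTX:

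- Schedule the Day 1, 8 and 43 visits around the subject's existing MTX day and time, without changing MTX dosing, so that all three samples fall at the same stated elapsed time after MTX and within the period when the assay can measure it. The sponsor should set that time from the assay limit and MTX kinetics; the table shows that even 24 h may be late if the half-life is short.
- State explicitly that the CRF captures the date, time and dose of the last MTX intake before the Day 1 sample.

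Assaying MTX in the 1, 2, 4 and 6 h draws would not be a substitute, since those are also timed to GSK2982772.

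The cost is protocol and CRF wording plus a scheduling constraint on three visits for MTX users, who would in practice have less use of the ±3 day window at Days 8 and 43. No extra visit is needed.

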## 7.2. Screening and Critical Baseline Assessments

After written informed consent, screening assessments will be performed as outlined in the Time and Events Table (Section 7.1).

The following demographic parameters will be captured: year of birth, sex, race and ethnicity.

Medical/medication/mental health and family history, ECG and laboratory tests will be assessed as related to the inclusion/exclusion criteria listed in Section 5.

Cardiovascular medical history/risk factors and smoking history (as detailed in the CRF) will be assessed at screening.

Patient Reported Outcomes questionnaires should be completed by subjects before any other assessment at a clinic visit, in the order specified in the SRM.

## 7.3. Safety

Planned time points for all safety assessments are listed in the Time and Events Table (Section 7.1). Additional time points for safety tests (such as vital signs, physical exams and laboratory safety tests) may be added during the course of the study based on newly available data to ensure appropriate safety monitoring.

The Investigator will be responsible for determining the clinical significance of any results that fall outside of the laboratory normal ranges.

In line with routine pharmacovigilance, an internal GSK Safety Review Team (SRT), which will include 203168 study team members, will review blinded safety data, including clinical laboratory parameters and adverse events, at appropriate intervals during the period of study conduct.

### 7.3.1. Adverse Events (AEs) and Serious Adverse Events (SAEs)

The definitions of an AE or SAE can be found in [Appendix 5](#).

The Investigator and their designees are responsible for detecting, documenting and reporting events that meet the definition of an AE or SAE.

#### 7.3.1.1. Time period and Frequency for collecting AE and SAE information

- Any SAEs assessed as related to study participation (e.g., protocol-mandated procedures, invasive tests, or change in existing therapy) or related to a GSK product will be recorded from the time a subject consents to participate in the study up to and including any follow-up contact.
- AEs will be collected from the start of Study Treatment until the follow-up contact (see Section 7.3.1.3), at the time points specified in the Time and Events Table (Section 7.1).

- Medical occurrences that begin prior to the start of study treatment but after obtaining informed consent may be recorded on the Medical History/Current Medical Conditions section of the CRF.
- All SAEs will be recorded and reported to GSK within 24 hours, as indicated in [Appendix 5](#).
- Investigators are not obligated to actively seek AEs or SAEs in former study subjects. However, if the Investigator learns of any SAE, including a death, at any time after a subject has been discharged from the study, and he/she considers the event reasonably related to the study treatment or study participation, the Investigator must promptly notify GSK.

NOTE: The method of recording, evaluating and assessing causality of AEs and SAEs plus procedures for completing and transmitting SAE reports to GSK are provided in [Appendix 5](#).

#### **7.3.1.2. Method of Detecting AEs and SAEs**

Care will be taken not to introduce bias when detecting AEs and/or SAEs. Open-ended and non-leading verbal questioning of the subject is the preferred method to inquire about AE occurrence. Appropriate questions include:

- “How are you feeling?”
- “Have you had any (other) medical problems since your last visit/contact?”
- “Have you taken any new medicines, other than those provided in this study, since your last visit/contact?”

#### **7.3.1.3. Follow-up of AEs and SAEs**

After the initial AE/SAE report, the Investigator is required to proactively follow each subject at subsequent visits/contacts. All SAEs, and non-serious AEs of special interest (as defined in Section 4.6.1) will be followed until resolution, until the condition stabilizes, until the event is otherwise explained, or until the subject is lost to follow-up (as defined in Section 5.4). Further information on follow-up procedures is given in [Appendix 5](#).

#### **7.3.1.4. Cardiovascular and Death Events**

For any cardiovascular events detailed in [Appendix 5](#) and all deaths, whether or not they are considered SAEs, specific Cardiovascular (CV) and Death sections of the CRF will be required to be completed. These sections include questions regarding cardiovascular (including sudden cardiac death) and non-cardiovascular death.

The CV CRFs are presented as queries in response to reporting of certain CV MedDRA terms. The CV information should be recorded in the specific cardiovascular section of the CRF within one week of receipt of a CV Event data query prompting its completion.

The Death CRF is provided immediately after the occurrence or outcome of death is reported. Initial and follow-up reports regarding death must be completed within one week of when the death is reported.

#### **7.3.1.5. Regulatory Reporting Requirements for SAEs**

Prompt notification by the Investigator to GSK of SAEs related to study treatment (even for non- interventional post-marketing studies) is essential so that legal obligations and ethical responsibilities towards the safety of subjects and the safety of a product under clinical investigation are met.

GSK has a legal responsibility to notify both the local regulatory authority and other regulatory agencies about the safety of a product under clinical investigation. GSK will comply with country specific regulatory requirements relating to safety reporting to the regulatory authority, Institutional Review Board (IRB)/Independent Ethics Committee (IEC) and Investigators.

Investigator safety reports are prepared for suspected unexpected serious adverse reactions according to local regulatory requirements and GSK policy and are forwarded to Investigators as necessary.

An Investigator who receives an Investigator safety report describing a SAE(s) or other specific safety information (e.g., summary or listing of SAEs) from GSK will file it with the IB and will notify the IRB/IEC, if appropriate according to local requirements.

